Informed consent will be obtained according to federal regulations and BCM and its affiliated hospital policies. Pregnant women will be informed of the objectives of this study by their obstetrician, primary nurse or study personnel at the time of the office visit during the third trimester of pregnancy.

The procedures involved will be described and the subjects will be asked if they would like to participate. The subjects will be made aware that there is no compensation for participation, and their care will not be altered as a result of their participation. No access to care will be withheld if subjects decline participation. Full disclosure of the nature of participating in the study will be made. The consent form will include a statement regarding long term storage of the samples. Subjects will be made aware their participation involves the analysis of genetic material, including the potential for genome wide association studies wherein the results of their DNA code will become part of public archives.

Subjects will further be made aware that confidentiality will be protected within the limits allowed by law. This will include using unique study identifier codes such that samples and data (including genetic data) cannot be linked to a subject or their child.

E3. Pregnant woman/fetus
Will pregnant women be enrolled in the research?

Yes

E4. Neonates

Will neonates be enrolled in the research?

Yes

E5. Children

Will children be enrolled in the research?

Yes

Section F: Design/Procedure

F1. Design

Select one category that most adequately describes your research:

c) Pilot

Discuss the research design including but not limited to such issues as: probability of group assignment, potential for subject to be randomized to placebo group, use of control subjects, etc.

This study is designed to collect a total of three sets of samples from women and their offspring in a feasibility study for formative research with the National Children's Study. Of note, all investigator obtained sample collection points correspond with existing visits within the currently approved NCS protocol ([name], PI).

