Briefly, samples for this formative project collected will include: 1. A vaginal specimen from pregnant women during their third trimester visit (existing time frame with current NCS protocol). 2. At the time of delivery, placental tissue and the infant's first meconium will be collected (existing time frame with current NCS protocol). 3. Subjects will be asked to submit a stool sample from their baby 1 month and 6 months after delivery.

In accordance with the NCS Protocol, subjects will be screened using a modified general health and pregnancy questionnaire and will be examined by an obstetrician-gynecologist at the time of sampling to verify eligibility. Subjects will be pregnant females between the ages of 18 and 40. Subjects who are 16 years old and meet the definition of an emancipated minor in the state of Texas will also be eligible for participation.

Eligible and consented subjects will be enrolled and the vaginal specimen will be collected at the time of the scheduled NCS protocol office visit during the third trimester. Each subject (defined as the gravidae) will provide a total of three sets of specimens: (1) vaginal swab for determination of the vaginal microbiome, taken at a single time point of 28 weeks gestation, (2) placental and fetal (meconium) swab, taken at the time of delivery (or shortly thereafter, dependent upon passage of first meconium sample), for determination of the placental and fetal microbiome. The infant stool samples at the one month and six month reference point will be collected at home using a self-collection kit and then sent to the investigator at Baylor College of Medicine.

Specific subject information will be collected via review of the medical record(s), with information being recorded on health history forms and study specific case report form (so-called NCS minimal data forms, see attachments). After specimen collection and coding, microbial DNA will be isolated from the microbiome specimens. The DNA will then be used to produce DNA sequence information (metagenomics) in accordance with fully functional and existing protocols through the Human Microbiome Project (H-25849, H-22895) and the Burroughs Wellcome Fund Preterm Birth Initiative (H-26589).

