RNA extraction: In order to assess potential feasibility of employing concomitant transcriptomics analysis in banked specimens, RNeasy or NucleospinII will be employed to extract RNA from the "banked approach" specimens. Given the timeline and expense associated with transcriptomics, demonstrative analysis will be deferred. Alternately, RNA yield and integrity will be assessed by standard Sybr and Nanodrop methodologies.

Metagenomic sequencing and analysis: All samples, whether collected and extracted at the BCM site or the WCVC site, will be shipped to BCM for metagenomic sequencing and analysis.

Sequencing overview: The predominant metagenomics sequencing strategy will focus on 16S rDNA 454 sequencing. This takes advantage of existing and fully functional technology and pipelines with proven reproducibility and quality reads in a self-sampled pediatric population. In addition to bacteria, archaea are surveyed by the addition of different primer sets to amplify archaeal 16S rDNA sequences, and fungi are identified by 18S rRNA gene/ITS-based sequencing. Sequencing of the bacterial 16S rRNA gene targets will be performed in collaboration with the existing HMP Genome Sequencing Centers (Baylor College of Medicine, Washington University Genomics Center, and the Broad Institute) by 454 GS Titanium sequencing. A detailed presentation of metagenomics DNA sequencing, informatics/biostatistics, and DNA sequencing approaches, is outside the scope of this protocol, but suffice it to say we are employing our present and proven methodology for sequencing, informatics pipelining, and analysis. All data are maintained on secure servers, in a coded (deidentified) fashion.

Bioinformatics overview: Read data will be filtered and analyzed so that accurate taxonomic assignments may be made while the HMP is completing its initial JumpStart phase, next-generation sequencing and analysis

approaches have been optimized, including our first analysis of 18 pregnant reference subjects (H-25849), and therefore further methodologic details are not included in this protocol.

Section G: Sample Size/Data Analysis

G1. Sample Size

How many subjects (or specimens, or charts) will be used in this study?

Local: 30 Worldwide: 120

Please indicate why you chose the sample size proposed:

This formative study seeks to evaluate feasibility of incorporating routine microbiome sampling as part of the National Children's Study (NCS).

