Subject confidentiality is strictly held in trust by the participating investigators, their staff, and the sponsor(s) and their agents. This confidentiality is extended to cover testing of biological specimens and genetic tests in addition to the clinical information relating to participating subjects. The study documentation, data and all other information generated will be held in strict confidence. No information concerning the study or the data will be released to any unauthorized third party without prior written approval of the sponsor. The study monitor or other authorized representatives of the sponsor may inspect all documents and records required to be maintained by the Investigator, including but not limited to, medical records (office, clinic or hospital) and pharmacy records for the subjects in this study. The clinical study site will permit access to such records.

Specifically, all data will be maintained in a deidentified fashion using unique generated study codes as previously described.

The nature of the information collected from subjects may involve risk to their privacy. This study will create a resource that will be available over the internet. The microbial DNA, which will be coded, will be deposited and be available through an open-access database. The clinical data will be available only through a NCS controlled-access database.

There is a small risk that some information could be disclosed to someone outside of the project or that, at some point, information stored in the controlled access databases could in some way be linked back to a specific subject. Despite the recent passage of a federal law that bars genetic discrimination in employment and some types of insurance, the use by others of genetic information from the eventual study of the blood specimens could conceivably impact the subject negatively in some way. For example, there is a very small risk that genetic information obtained by this study could be used by law enforcement officials to try to learn more about the subjects or their family members for the purpose of a criminal investigation. However, anyone seeking access to the information in the controlled access databases will need prior approval of site investigators.

Who, besides the PI, the study staff, the IRB and the sponsor, will have access to identifiable research data?

Access to study specific records will be limited to the PI, study personnel and appropriate regulatory agencies.

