Will you obtain a Certificate of Confidentiality for this study?

No

Please further discuss any potential confidentiality issues related to this study.

Section L: Cost/Payment

Delineate clinical procedures from research procedures. Will subject's insurance (or subject) be responsible for research related costs? If so state for which items subject's insurance (or subject) will be responsible (surgery, device, drugs, etc). If appropriate, discuss the availability of financial counseling.

Patients will not be charged to participate and all ensuant costs to the research will be covered by the study grant.

If subjects will be paid (money, gift certificates, coupons, etc.) to participate in this research project, please note the total dollar amount (or dollar value amount) and distribution plan (one payment, pro-rated payment, paid upon completion, etc) of the payment.

Dollar Amount:

100

Distribution Plan:

Single payment following receipt of final specimen. In instances of fetal or neonatal or infant demise, remuneration will occur with last specimen received.

The rationale for deferring payment until the final specimen is received, rather than by study visit, is that the design of the study requires complete data sets.

Section M: Genetics

How would you classify your genetic study?

Discuss the potential for psychological, social, and/or physical harm subsequent to participation in this research. Please discuss, considering the following areas: risks to privacy, confidentiality, insurability, employability, immigration status, paternity status, educational opportunities, or social stigma.

Not applicable, as this a microbiome metagenomics study and host DNA is not analyzed.

Will subjects be offered any type of genetic education or counseling, and if so, who will provide the education or counseling and under what conditions will it be provided? If there is the possibility that a family's pedigree will be presented or published, please describe how you will protect family member's confidentiality?

Not applicable.

Section N: Sample Collection

SAMPLE: Other: Vagina

What is the purpose of the sample collection?

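### Section E2 tells women their own DNA may enter genome-wide studies and public archives, while Section M says host DNA is not analysed and skips the genetic-harm question

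*Protocol*

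**What the plan says.** Section E2, under protections for vulnerable populations, sets out what women will hear before they agree. It mentions genetic analysis in general and then widens this to their own genome: "including the potential for genome wide association studies wherein the results of their DNA code will become part of public archives".

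Section M (Genetics) asks about psychological, social and physical harm, and names privacy, insurability, employability, paternity status and stigma among the areas to consider. The whole answer is: "Not applicable, as this a microbiome metagenomics study and host DNA is not analyzed". The next question, on genetic education and counseling, is also marked as not applicable.

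The procedures concern microbes. Section F1 states: "After specimen collection and coding, microbial DNA will be isolated from the microbiome specimens". Section F2 adds: "The predominant metagenomics sequencing strategy will focus on 16S rDNA 454 sequencing", with further primers for archaea and marker-gene sequencing for fungi.

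Section K limits open release: "The microbial DNA, which will be coded, will be deposited and be available through an open-access database". Clinical data go to a controlled-access database. The same section then warns that "the use by others of genetic information from the eventual study of the blood specimens could conceivably impact the subject negatively in some way". Section N answers the blood-draw question as not applicable for all three sample types: vaginal, placental and stool.

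**The concern.** The protocol gives incompatible accounts of whose DNA is analysed and what becomes public. A woman who hears the E2 statement would understand that her own genome might be studied and published. A reviewer who reads Section M would understand that no human genetic data arise, and would therefore expect no discussion of harm.

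What is at stake is participant protection. The people enrolled include pregnant women, emancipated minors and newborns, whom the protocol itself lists as needing special protection, and the study is submitted under the minimal-risk category. Both the disclosure and that risk category should rest on one account of what is done with the DNA. At present, following the protocol means either disclosing a risk that the study does not carry, or doing host-DNA work for which the harm question was set aside.

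**Working it through.** No formula applies and the plan gives no figure to reproduce. The check sets the statements side by side.

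| Section | Whose DNA is analysed | What is released, or what risk is named |
|---|---|---|
| E2 | The subjects' own, potentially genome-wide | Results go to public archives |
| F1, F2 | Microbial; no host genotyping described | Release not covered here |
| K, on release | Microbial | Coded microbial DNA, open access |
| K, on risk | Genetic information from blood | Discrimination, law-enforcement use |
| M | Host DNA excluded | Harm question set aside |
| N | Vaginal, placental and stool samples; no blood | Release not public; stool shared only within the NCS, coded |

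**Step 1: can E2 and M both be true?** E2 speaks of a potential for such studies, which is weaker than a plan to do them. Section M, however, excludes host DNA without reservation, so even a potential contradicts it. Nor does the possessive in E2 read naturally as microbial DNA: the sentence is about the subjects and about genome-wide association studies. No other section limits it to microbes or assigns it to a separate study.

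**Step 2: which side do the methods support?** They support Section M. F1 isolates microbial DNA. F2 targets bacterial, archaeal and fungal marker genes. RNA from banked specimens is checked only for yield and integrity, and transcriptomic analysis is deferred. Filing the placental swabs under a genetic-material heading in Section N does not change this, because their stated purpose is microbiome profiling.

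**Step 3: does K settle the matter?** It does not. Its release rule agrees with the methods, but its risk text refers to a specimen that the study does not take.

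**Step 4: what follows from each reading?**
- Microbial only: the genome statement in E2 and the blood text in K describe risks from work that is not done.
- Host DNA intended: F1 and F2 omit the work, and Section M's answers on harm and counseling are wrong.

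Either way, at least one section must change.

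**Step 5: how many women are clearly covered?** Section G1 gives 30 at BCM and 90 at the Waukesha site: 30 + 90 = 120. Section F1 says the second site works under its own IRB protocol. The text at hand therefore clearly governs 30 of 120, or 30/120 = 25%, together with their infants.

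**The case against.** The strongest reply is that this is an inconsistency of documentation in a minimal-risk pilot. The actual procedures are clear, and Section K does address re-linkage, discrimination in employment and insurance, and law-enforcement interest. Much of that stands. The methods are indeed unambiguous, and it would be too strong to infer that genetic risk is left unassessed. Section K covers it in part; paternity status and stigma, which Section M asks about, are not covered there.

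Four further inferences are tempting and are not supported.

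- **That consent is defective.** The two consent forms listed in Section Q are not shown. What can be said is that the protocol's account of the disclosure conflicts with other sections.
- **That all 120 women are affected.** Section H3 says the BCM approval will be forwarded to Wisconsin, but nothing shows that the E2 text governs disclosure at a site with its own IRB protocol.
- **That uptake, and so the feasibility result, would be distorted.** Neither the primary objectives in Section D nor the comparisons in Section G2 measure consent or refusal, and the protocol gives no refusal rate. BCM needs 30 women from about 900 potential subjects a year (30/900 = 3.3%).
- **That a human-read filter or a fresh-consent rule for banked samples is missing.** Section D banks specimens for future microbiome metagenomics, and Section N requires IRB approval and a transfer agreement before stool goes to other NCS investigators. Section F2 says reads will be filtered and leaves informatics detail outside the protocol. Such rules would be new policy and are not needed to remove the contradiction.

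The objection does not remove the direct conflict between E2 and M, or K's reference to blood.

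**Conclusion.** The point holds as a contradiction in the current protocol text that bears on participant protection. E2 commits staff to telling women about possible genome-wide study and public archiving of their own DNA. Section M says host DNA is not analysed and on that basis declines the harm question. Section K adds a blood specimen that Section N does not collect.

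Its demonstrable reach is the 30 BCM women and their infants. It has no numerical consequence: sample size, power and error rates are untouched. The conclusion assumes that Sections F1 and F2 are a complete account of the laboratory work, and that the E2 statement will be conveyed to women as described. It should be corrected because the correction is cheap and changes what women are told.

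**What to change.** Decide whether host DNA is to be analysed, then make E2, K and M say the same thing.

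- **If only microbial DNA is analysed, as the methods state:** replace the genome-wide statement in E2 with one saying that only microbial sequence is analysed and deposited. Remove the blood-specimen wording from K, and check that the law-enforcement example that follows refers to information the study will hold. Section M's exclusion of host DNA can then stand. Match the consent forms to the corrected text.
- **If host DNA analysis is intended:** describe it in F1 and F2, and answer Section M's questions on harm and counseling in substance. K should then name the specimen actually used.

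The first route costs a few sentences of protocol and consent text and the amendment to carry them. The second costs more, because the host work and its risks would have to be written up and reviewed. Neither route alters sampling, sequencing or the number of women enrolled, unless the intended host work itself requires it.

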Placental sample collection: At the time of delivery, a CatchAll® swab will be employed under direct visualization to sample in triplicate the placenta on the fetal side in a uniform fashion (4 cm medial to the cord insertion). In the scientific protocol, nucleic acid is again stored in SCF-1 buffer media and transported to the laboratory for immediate extraction. In the "banking approach", samples will be placed into either (1) RNeasy

or (2) SCF-1 media, and thereafter placed on dry ice and stored at -80oC. At approximately 60 days from sample acquisition, nucleic acid extraction will be performed on both banking protocol samples in a replicate cohort (10%).

Meconium and stool sample collection: First meconium samples will be collected in the diaper. For longitudinal stool sample collection, subjects will be instructed to perform self-collection of fecal specimens at home. In addition, a portion of the fecal specimen will be preserved in RNAlater as part of the specimen banking protocol. Briefly, in this demonstration project children and their or guardians will receive at least two sterile plastic collection containers with plastic stool collection frames. They will be instructed to place stool collection frames on the back of the toilet bowl prior to securing the stool container. After defecation, a portion of the specimen will be placed into RNAlater for preservation and banking protocol, and then the stool container will be closed firmly with a plastic lid and placed into a Styrofoam box with cold gel packs. Eight to ten polar gel packs per fecal specimen will be stored for a maximum of 12 hours in a freezer (at subject's home) prior to stool collection. Gel packs will be placed below and around (completely surrounding) stool container within the Styrofoam box. This box will be delivered to the laboratory for immediate nucleic acid extraction. The RNAlater sample will be stored at -80oC. At approximately 60 days from sample acquisition, nucleic acid extraction will be performed on both banking protocol.

DNA extraction: For fresh extraction, samples will arrive in PowerBead tubes provided. For banked approach samples, initial thawing on ice with subsequent sample addition to PowerBead tubes. Nucleic acid is freed with extensive vortexing, and subsequent transfer of supernatant to collection tubes for extraction using filter-based centrifugation in a modified MoBio protocol (HMP MOP, available upon request).

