The majority of sample collection (90 of 120 subjects) will take place at WVCV, where participant enrollment began in 2008 and averages 10 to 12 NCS births per month with anticipated increasing accrual. A smaller cohort of participants (30 of 120 subjects) will be enrolled at BCM.

BCM, although not currently enrolling in the Vanguard pilot, has established and optimized approaches for microbial sampling of vagina, placenta, meconium, and feces, through participation in the HMP JumpStart and HMP Clinical Demonstration Project (UH2) initiatives and will thus serve as a measured control against any methodological concerns related to microbial sampling and nucleic acid extraction (see prior referenced IRB approved protocols).

The combined involvement of these sites will leverage the NCS experience and extensive environmental data collection of WVCV with the HMP metagenomics infrastructure at BCM, and allow us to evaluate the feasibility of adding microbiome sampling and metagenomic analysis to the NCS.

G2. Data Analysis

Provide a description of your plan for data analysis. State the types of comparisons you plan (e.g. comparison of means, comparison of proportions, regressions, analysis of variance). Which is the PRIMARY comparison/analysis? How will the analyses proposed relate to the primary purposes of your study?

Outline of goals and strategies for the collection, analysis, and characterization of metagenomics data from NCS acquired specimens employing established methodology from the HMP JumpStart initiative have been previously outlined.

Briefly, our collaborative proposal will use a two layered analysis strategy.

We will collect microbial specimens (n=120 gravidae, 90 from WVCV and 30 from BCM) at NCS specified timepoints, and aliquot specimens for both fresh extraction and banked specimen protocols. We will extract nucleic acids from at the time of specimen collection and subsequently subject such immediate extractions to flash freezing for later batched-run metagenomic sequencing and analysis. In the second-layer strategy, we will collect parallel samples from each subject for immediate banking (using 1 of 2 "banking" protocols) rather than already proven immediate nucleic acid extraction. A randomly-selected cohort comprising 20% (10% of each of

the two banking protocols) of these “banked” specimens will be run in batched parallel samples in order to establish and refine banking methodology.

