For neonates of uncertain viability: The legally effective informed consent will be obtained of either parent of the neonate, except that the consent of the father or his legally authorized representative need not be obtained if the pregnancy resulted from rape or incest (If neither parent is able to consent because of unavailability, incompetence, or temporary incapacity, the legally effective informed consent of either parent's legally authorized representative will be obtained, except that the consent of the father or his legally authorized representative need not be obtained if the pregnancy resulted from rape or incest) Each individual providing consent will be fully informed regarding the reasonably foreseeable impact of the research on the neonate.

For longitudinal sampling, subjects will be called and reminded, with "self" (parental) sampling as detailed previously.

Are foreign language consent forms required for this protocol?

No

J3. Privacy and Intrusiveness

Will the research involve observation or intrusion in situations where the subjects would normally have an expectation of privacy?

No

J4. Children

Will children be enrolled in the research?

Yes

J5. Neonates

Will non-viable neonates or neonates of uncertain viability be involved in research?

Yes

J6. Consent Capacity - Adults who lack capacity

Will Adult subjects who lack the capacity to give informed consent be enrolled in the research?

No

J7. Prisoners

Will Prisoners be enrolled in the research?

No

Section K: Confidentiality

Will research data include health information by which subjects can be identified?

Yes

Where will research data be kept? How will such data be secured?

The research data will be stored on a secure server at BCM. Once samples are collected identifiers are removed and only the Study ID will be retained. Subject's data is maintained on certified NCS servers, and all sequencing data is maintained in a coded (deidentified) fashion on secure servers.

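### The only home stool capture step in the protocol needs a toilet, but every home donor is an infant aged 1 or 6 months, and no infant method is given for these stools

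*Protocol*

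**What the plan says.** Section F1 (Design) fixes the donors and their ages: "Subjects will be asked to submit a stool sample from their baby 1 month and 6 months after delivery". It also fixes the setting: "The infant stool samples at the one month and six month reference point will be collected at home using a self-collection kit". Section D lists self-sampled stool at one and six months under Primary Objective 1, and the tissue entry in Section N repeats the two ages. Section J2 says that the self-sampling is done by the parent, and for the method it points back to the earlier description.

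That description is in Section F2 (Procedure), under meconium and stool. Families are issued at least two sterile containers together with plastic collection frames, and then: "They will be instructed to place stool collection frames on the back of the toilet bowl prior to securing the stool container". Once the child has passed stool, a portion goes into RNAlater, the container is lidded and surrounded with cold gel packs, and the box goes to the laboratory. The same paragraph names the diaper once, for a different specimen: "First meconium samples will be collected in the diaper".

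On numbers, Section G1 gives "Local: 30 Worldwide: 120" and Section G2 says "We will collect microbial specimens (n=120 gravidae, 90 from WVCV and 30 from BCM) at NCS specified timepoints". Section F1 adds that the second enrolling site works under an IRB protocol of its own.

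**The concern.** A frame resting on a toilet bowl presupposes a child who uses a toilet. At 1 and 6 months none does. The written step therefore does not match the donor ages set in Sections D, F1 and N, and the back-reference in Section J2 leads only to that same step.

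The study exists to show whether microbiome sampling can be added to a large cohort, and home stool sampling is part of its first primary objective. If the stated capture step cannot be performed, a collected sample says nothing about whether the written procedure works, and a missing one cannot be read clearly as a failure of feasibility. Parents would need some other way to obtain the stool, and because the protocol fixes none, that way could differ from family to family and from site to site. Section G1 casts BCM as the methodological control for sampling and extraction, so the gap lies in the reference site's own procedure. Section H3 says that no protocol modifications will be made, so the plan does not foresee a correction once the study is running.

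**Working it through.** No sample-size formula applies. The check sets the passages side by side and then counts.

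**Step 1: who gives stool at home, and who takes it.**
- Ages: 1 month and 6 months (Sections D, F1, N).
- Collector: the parent (Section J2).
- No older child gives stool anywhere in the protocol.

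**Step 2: which capture methods are written down.**

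| Specimen | Capture method in the protocol | Usable at that age? |
|---|---|---|
| First meconium | in the diaper (F2); swab (F1) | yes |
| 1-month stool | frame on toilet bowl (F2) | no |
| 6-month stool | frame on toilet bowl (F2) | no |

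The sequencing overview in F2 mentions proven results in self-sampled children but gives no age, so it supplies no infant method.

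**Step 3: which steps fail.** Only the capture step depends on a toilet. The RNAlater portion, the lid, the gel packs, delivery for immediate extraction and storage at -80°C do not.

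**Step 4: how many samples.**
- The plan's own total: 30 (BCM) + 90 (second site) = 120 women, which reproduces the stated 120.
- Planned home stools = women x 2 time points, assuming one infant per woman and no loss. The protocol states no stool total, so these counts are derived:
  - BCM, governed by this text: 30 x 2 = 60.
  - Second site, under its own protocol: 90 x 2 = 180.
  - Both sites: 120 x 2 = 240, of which BCM is 60/240 = 25%.
- The protocol gives no loss rate. For assumed losses of 0% to 30%:

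| Assumed loss | BCM | Both sites |
|---|---|---|
| 0% | 60 | 240 |
| 10% | 54 | 216 |
| 20% | 48 | 192 |
| 30% | 42 | 168 |

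**Step 5: share of the study's material.** There are five specimen types: vaginal, placental, meconium, 1-month stool and 6-month stool. The capture step concerns two of the five, and all of the home-collected material at BCM.

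**The case against.** The strongest reply is that the F2 paragraph is offered as a brief summary and that the kit's own instructions are not shown. They might describe an infant method. That would excuse missing detail. It does not excuse a stated step that cannot be done, and the paragraph says that the frames themselves are supplied to families in this project. What stands is that improvisation by every family is a possibility, not something the protocol shows.

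Several stronger readings are tempting, and the document does not support them.

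- **All 240 stools would be collected off protocol.** The second site has its own IRB protocol. Section H3 says that the approved BCM document will be sent to Wisconsin, so the text may carry over, but this is not shown. Only the 60 BCM stools are certainly covered.
- **The whole written method is inapplicable.** Only the capture step fails; the handling steps that follow it can be done.
- **Meconium collection is contradictory.** F1 speaks of a "placental and fetal (meconium) swab, taken at the time of delivery" and F2 of the diaper. A swab taken from the diaper satisfies both, and nothing requires meconium and later stools to share a method.
- **The longitudinal gut comparison is biased by infant age.** Section G2 lists comparisons of read length and quality, of taxonomic assignment, and of their variation with delivery mode, BMI and feeding. It lists none across meconium, 1 month and 6 months. The two home stools also share one kit and one instruction.
- **The fresh-versus-banked contrast is compromised.** F2 already takes the preserved portion from the same stool, so whatever happens before the split is largely shared within the pair. This also removes the case for requiring handling time as a covariate.

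**Conclusion.** The point holds for the capture step. The protocol's only home capture method cannot be used with its only home donors, and no infant method is given for them. This reaches all 60 planned home stools at BCM, and up to 240 if the second site's protocol carries the same text. Both figures assume one infant per woman and no loss.

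The consequence is that this part of Primary Objective 1 cannot be tested as written, and that capture could vary between families and sites. The size of that variation cannot be computed from the document. Sample size, eligibility and the named comparisons are unaffected.

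**What to change.** In the stool paragraph of Section F2 and in the kit, replace the toilet-frame instruction and the frames with one stated diaper-based method for parents to use at 1 and 6 months, for example a sterile scoop or a sterile liner. Keep the existing RNAlater portion and the cold-pack steps as they are. Use the same method at both sites, which means checking the second site's protocol and aligning it if it carries the frame text. Make the change before kits are issued.

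The cost is one rewritten paragraph, a revised kit insert and scoops or liners in place of frames.
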